1.3. Schedule of Activities

Table 1: Schedule of Activities

	BL ^a	Study week																EDV ^b	SFV ^c
		1	2	3	4	5-7	8	9-11	12	13-15	16	17-23	24	25-35	36	37-47	48		
Study day (±2)	1	8	15	22	29	36-50	57	64-78	85	92-120	127	134-162	169	176-246	253	260-330	337		393
Note: All activities (safety and efficacy assessments, predose blood sampling) will be completed before administering the IMP infusion.																			
Visits that must be attended at the site are BL, W1 (for QW regimen), W2, W4, W8, W12, W16, W24, W36, W48, EDV, and SFV. Additionally, participants must attend visits at the site for their first 3 doses of efgartigimod in this OLE study. All other visits may be conducted by home health care service or telemedicine visit.																			
Informed consent	X																		
Eligibility check	X																		
Brief physical examination (symptom driven)	X ^d				X		X		X		X		X		X		X	X	X
Vital signs ^e	X				X		X		X		X		X		X		X	X	X
ECG	X				X		X		X		X		X		X		X	X	X
Glandular function																			
UWSE/SWSF	X										X		X		X		X	X	
Schirmer's test	X										X		X		X		X	X	

	BL ^a	Study week																EDV ^b	SFV ^c
		1	2	3	4	5-7	8	9-11	12	13-15	16	17-23	24	25-35	36	37-47	48		
Study day (±2)	1	8	15	22	29	36-50	57	64-78	85	92-120	127	134-162	169	176-246	253	260-330	337		393
OSS	X										X		X		X		X	X	
SGUS	X										X		X		X		X	X	
Safety laboratory assessments																			
Clinical laboratory tests (hematology and chemistry)	X				X		X		X		X		X		X		X	X	X
Urinalysis	X										X		X		X		X	X	X
Urine pregnancy testing	X																	X	X
Blood sampling																			
CCI																			
PK ^h	X ⁱ				X		X		X		X ⁱ		X		X		X		
Total IgG ^f	X				X		X		X		X		X		X		X		X
RF ^f	X				X						X		X		X		X		X
Anti-Ro/SS-A, anti-La/SS-B autoantibodies ^f	X				X		X		X		X		X		X		X		X

	BL ^a	Study week																EDV ^b	SFV ^c
		1	2	3	4	5-7	8	9-11	12	13-15	16	17-23	24	25-35	36	37-47	48		
Study day (±2)	1	8	15	22	29	36-50	57	64-78	85	92-120	127	134-162	169	176-246	253	260-330	337		393
Immunogenicity ^f	X		X		X		X		X		X		X		X		X		X
Systemic disease activity																			
ESSDAI ^f	X										X		X		X		X		
clinESSDAI	X										X		X	W32 ^k	X ^k	W40, W44 ^k	X		
Patient-reported outcome questionnaires^l																			
ESSPRI	X										X		X		X		X		
MFI	X										X		X		X		X		
PGA	X										X		X		X		X		
SF-36	X										X		X		X		X		
EQ-5D-5L	X										X		X		X		X		
PASS	X												X				X		

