IMP infusion ^m	X ⁿ	X ^{o,p}																	
AE review	Continuous monitoring																		
Concomitant medications review	Continuous monitoring																		

	BL ^a	Study week																EDV ^b	SFV ^c
		1	2	3	4	5-7	8	9-11	12	13-15	16	17-23	24	25-35	36	37-47	48		
Study day (±2)	1	8	15	22	29	36-50	57	64-78	85	92-120	127	134-162	169	176-246	253	260-330	337		393

BL = baseline; clinESSDAI = clinical; ESSDAI; D = day; d/c = discontinuation; ECG = electrocardiogram; EDV = early discontinuation visit; ESSDAI = EULAR Sjögren’s syndrome disease activity index; ESSPRI = EULAR Sjögren’s Syndrome Patient-Reported Index; EULAR = European Alliance of Associations for Rheumatology; ICF = informed consent form; IgG = immunoglobulin G; IMP = investigational medicinal product; IV = intravenous; MFI = Multidimensional Fatigue Inventory; NA = not applicable; OSS = ocular staining score; PASS = patient acceptable symptom state; PCR = polymerase chain reaction; PD = pharmacodynamics; PGA = patient global assessment; PK = pharmacokinetics; RF = rheumatoid factor; SCR = screening; SFV = safety follow-up visit; SF-36 = 36-Item Short Form Survey; SGUS = salivary gland ultrasonography; SS-A = Sjögren’s syndrome-related antigen A; SS-B = Sjögren’s syndrome-related antigen B; SWSF = stimulated whole salivary flow; UWSF = unstimulated whole salivary flow; W = week.

^a BL will coincide with the final visit of a previous qualifying study. Grayed-out assessments may be conducted as part of the previous qualifying pSS studies.

^b The EDV will be performed within 7 days after last dose administration.

^c Participants will attend a safety follow-up visit 56 ± 3 days after the final IMP administration.

^d Weight mandatory at baseline.

^e Vital signs will be measured before collecting any blood sample or administering IMP infusions.

^f On IMP administration visits, blood samples must be collected predose (preferably within 2 hours before the infusion). On other visits, a blood sample may be collected at any time during the visit.

^h On IMP administration visits, blood samples for PK analyses will be collected predose (preferably within 2 hours before IMP administration). On other visits, a blood sample may be collected at any time during the visit.

ⁱ A PK sample will also be collected within 30 minutes after the end of IMP infusion.

^j The biological domain will remain blinded until the parent study is unblinded.

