5.1. Inclusion Criteria

Participants can be included in the study only if all of the following criteria apply:

1. Is at least the legal age of consent for clinical trials when signing the ICF
2. Is capable of providing signed informed consent, as described in Section 10.1.3, and complying with protocol requirements
3. Agrees to use contraceptive measures consistent with local regulations and the following:
 - a. WOCBP (defined in Section 10.4.1) must have a negative urine pregnancy test at baseline before receiving IMP (Section 10.4.2.1)
4. Has completed the qualifying efgartigimod pSS studies and agrees to continue study drug treatment without interruption in the extension study

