7.1. Discontinuation of IMP

7.1.1. Permanent Discontinuation

Permanent discontinuation of IMP occurs when the participant stops receiving the IMP before the end of the study, does not resume receiving IMP, and does not withdraw informed consent.

The investigator will document the primary reason for early discontinuation of IMP.

Participants who permanently discontinue IMP will complete the EDV.

The study sites will attempt to perform the EDV within 7 days after the participant's final IMP administration. The SFV will occur 56 ± 3 days after the participant's final IMP administration.

Additionally, the following circumstances will result in the permanent discontinuation of IMP:

- The participant becomes pregnant or intends to become pregnant (see Section 8.3.5)
- The investigator considers discontinuing IMP is in the participant's best interest (the sponsor will be informed)
- The participant develops an SAE or AE that contraindicates further administration of IMP in the investigator's opinion or an AE of CTCAE severity grade 4 that is considered related to IMP by the sponsor
- The participant develops a new or recurrent malignancy except for basal cell carcinoma of the skin, regardless of relationship to IMP
- The participant receives a prohibited medication or substance (Section 6.9)

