8.3.5. Pregnancy Testing

- WOCBP will be tested for pregnancy. Urine tests for pregnancy will occur at the time points specified in the SoA (Section 1.3)
- Pregnancy testing in WOCBP will be conducted at the end of relevant systemic exposure (ie, at the SFV)
- Additional pregnancy testing could be performed, as deemed necessary by the investigator or required by local regulations, to establish the absence of pregnancy at any time during the study

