8.4.5. Pregnancy

- If pregnancy is reported, the investigator will record the pregnancy information on the appropriate form and submit it to the sponsor within 24 hours of learning of the pregnancy in the female participant or the female partner of the male participant. Contact details are provided in [Serious Adverse Event Reporting](#)
- The participant and pregnant female partner, if consented (Section [10.1.3](#)), will be followed to determine the outcome of the pregnancy. The investigator will collect follow-up information on the participant/pregnant female partner and the neonate and forward it to the sponsor
- While pregnancy itself is not considered an AE or SAE, any pregnancy complication or elective termination of a pregnancy for medical reasons will be reported as an AE or SAE. Abnormal pregnancy outcomes (eg, spontaneous abortion, fetal death, stillbirth, congenital anomalies, ectopic pregnancy) are considered SAEs and will be reported accordingly
- Any poststudy pregnancy-related SAE considered reasonably related by the investigator to IMP will be reported to the sponsor as described in Section [8.4.4](#)
- Any female participant who becomes pregnant during the study will discontinue IMP

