10.2. Appendix 2: Clinical Laboratory Tests

- The tests listed in [Table 6](#) will be performed as described in the Laboratory Manual
- Additional tests can be performed during the study as determined necessary by the investigator or required by local regulations
- Investigators must document their review of each laboratory test result

Table 6: Protocol-Required Laboratory Tests

Laboratory Test	Parameters		
Hematology	RBC count platelet count hemoglobin hematocrit	RBC indices: MCV MCH %reticulocytes	WBC count with differential: neutrophils eosinophils lymphocytes basophils monocytes
Serum chemistry	ALT AST GGT alkaline phosphatase albumin ^a	creatinine potassium BUN CRP glucose	sodium total protein ^a calcium bilirubin (total and direct)
Routine urinalysis	Specific gravity pH, glucose, protein, blood, ketones, bilirubin, urobilinogen, nitrite, leukocyte esterase Microscopic examination (if blood or protein is abnormal)		
Pregnancy testing	Urine test at baseline and other time points (as needed for WOCBP potential, defined in Section 10.4.1)		

ALT = alanine aminotransferase; AST = aspartate aminotransferase; BUN = blood urea nitrogen; CRP = C-reactive protein; GGT = gamma-glutamyl transferase; MCH = mean corpuscular hemoglobin; MCV = mean corpuscular volume; RBC = red blood cell; WBC = white blood cell

^a This result will be blinded baseline and up to the week 4 (day 29) visit.

10.3. Appendix 3: AEs and SAEs: Definitions and Procedures for Recording, Evaluating, Follow-up, and Reporting

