10.4.2. Contraception Guidance

10.4.2.1. Female Contraception for Women of Childbearing Potential

WOCBP must use one of the following contraception methods from signing the ICF until the last dose of IMP.

The following Clinical Trials Facilitation and Coordination Group¹⁷ acceptable methods are permitted for efgartigimod studies:

- Progestogen-only oral hormonal contraception in which inhibition of ovulation is not the primary mode of action
- Male or female condom with or without spermicide
- Cap, diaphragm, or sponge with spermicide

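### Pregnancy is a mandatory stop for IMP, yet after baseline no pregnancy test is planned in 46 to 47 weeks of dosing; urine tests at weeks 16, 24 and 36 would close most of the gap.

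*Protocol*

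**What the plan says.** Pregnancy ends treatment. Protocol Section 7.1.1 lists it among the reasons for permanent discontinuation and refers the reader to Section 8.3.5 (Pregnancy Testing). Section 8.4.5 repeats the rule: "Any female participant who becomes pregnant during the study will discontinue IMP". Inclusion criterion 3 (Section 5.1) adds that WOCBP "must have a negative urine pregnancy test at baseline before receiving IMP".

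In Table 1 (Section 1.3) the row "Urine pregnancy testing" is marked at baseline, EDV and SFV and is blank from week 1 to week 48. The urinalysis row just above it is marked at weeks 16, 24, 36 and 48. SAP Section 6.3 agrees: its pregnancy-test window table has baseline and safety follow-up only. On the EDV, footnote b of Table 1 says: "The EDV will be performed within 7 days after last dose administration". The SFV is 56 ± 3 days after the final dose.

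Two provisions bear on the time in between. Section 8.3.5 states: "Additional pregnancy testing could be performed, as deemed necessary by the investigator or required by local regulations"; Table 6 (Section 10.2) likewise leaves later urine tests to need. Section 10.4.2.1 states: "WOCBP must use one of the following contraception methods from signing the ICF until the last dose of IMP".

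**The concern.** The stop rule acts only once someone knows of the pregnancy, and the schedule plans nothing during treatment that would reveal one. EDV and SFV look back after dosing has ended. The EDV also applies only to participants who stop IMP early, so a completer's only planned post-baseline test is the SFV.

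In between, detection depends on the participant reporting a pregnancy, on an investigator choosing to test, or on a local requirement. An early, unrecognised pregnancy could therefore be exposed to further infusions that the protocol means to prevent, and practice may differ between sites and countries.

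The sections do not contradict one another. What is missing is a planned test during treatment. No endpoint, analysis set or estimate is affected.

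**Working it through.** **Inputs**
- Final dose: week 47 on QW, week 46 on Q2W (Protocol Section 1.2 and Table 1 footnote o).
- SFV: 56 ± 3 days after the final dose (Table 1 footnote c).
- Planned tests for a completer: baseline and SFV (Table 1; SAP Section 6.3).
- Mandatory site visits include weeks 16, 24 and 36 (Table 1).

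**Day convention.** Study day = 7 × week + 1. Week 47 is then 7 × 47 + 1 = 330, which matches the upper end of the Table 1 column for weeks 37-47 (days 260-330). Week 46 is day 323.

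**As planned**
- QW: SFV on day 330 + 56 = 386. Interval between planned tests: 386 − 1 = 385 days (382 to 388 with the ±3-day window). Dosing span: 330 − 1 = 329 days. Infusions at weeks 0 to 47 number 48, so 47 follow the day-1 dose.
- Q2W: SFV on day 323 + 56 = 379. Interval: 378 days (375 to 381). Dosing span: 322 days. Infusions at even weeks 0 to 46 number 24, so 23 follow the day-1 dose.

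Table 1 prints the SFV as day 393, which is week 48 (day 337) + 56. Counted that way the interval is 392 days; the conclusion is the same.

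**With predose tests at weeks 16, 24 and 36**

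| Stretch | Weeks of dosing | Infusions after the test-day dose, QW | Same, Q2W |
|---|---|---|---|
| Baseline to week 16 | 16 | 15 | 7 |
| Week 16 to 24 | 8 | 7 | 3 |
| Week 24 to 36 | 12 | 11 | 5 |
| Week 36 to last dose | 11 (QW), 10 (Q2W) | 11 | 5 |

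The longest run of infusions without a new planned test falls from 47 to 15 (QW) and from 23 to 7 (Q2W). The longest untested stretch of dosing falls from 329 or 322 days to 16 × 7 = 112 days. Week 16 is taken here as day 113, as in SAP Section 6.3. With the day 127 printed in Table 1, the stretch is 126 days.

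**Average effect.** Assume conception is equally likely at any time during dosing. The mean dosing time from conception to the next planned test or the last dose is the sum of squared stretches divided by twice the dosing weeks.
- QW: as planned, 47² / (2 × 47) = 23.5 weeks; with the added tests, (16² + 8² + 12² + 11²) / 94 = 585 / 94 = 6.2 weeks.
- Q2W: as planned, 23.0 weeks; with the added tests, (16² + 8² + 12² + 10²) / 92 = 564 / 92 = 6.1 weeks.

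That is a reduction of about 73% on both regimens.

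**What remains.** The first 16 weeks stay untested. The interval from week 36 to the SFV is 386 − 253 = 133 days (QW) or 379 − 253 = 126 days (Q2W), of which the last 56 days are off treatment.

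**The case against.** The strongest reply is that testing during treatment was delegated on purpose. Section 8.3.5 and Table 6 let the investigator test at any time, and a country that requires periodic testing already triggers it. Contraception is mandatory. Participants are dosed every one or two weeks, and at each home visit the investigator or designee interviews the participant by audio or video (Appendix 6), so there are many occasions to prompt a test. The risk table in Section 2.3.1 lists no embryo-fetal risk, and the number of WOCBP is not given. The 385 days describe test spacing; they exceed the length of a pregnancy and cannot be read as a realistic delay to detection.

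Much of this stands as a limit on weight. The figures measure how long the schedule goes without a test. They do not give an expected number of exposed pregnancies, which cannot be estimated from these documents. The reply does not remove the gap: discretion sets no minimum, contraception lowers the risk without detecting failures, and the home-visit interview covers adverse events, medications and well-being without naming pregnancy. The protocol itself treats pregnancy as serious enough to require a negative test before the first dose and to end treatment.

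A second objection is that a first added test at week 16 is late for an early pregnancy. That is fair, and the 15 untested QW infusions before it show it. Weeks 4, 8 and 12 are also site visits and could be used.

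**Conclusion.** The point holds. After baseline, no planned pregnancy test falls within the 46 to 47 weeks of dosing, although pregnancy is a mandatory reason to stop. For a completer, 47 (QW) or 23 (Q2W) infusions follow the baseline test day with no planned test. Three added tests would cut the longest run to 15 or 7 and the longest untested stretch of dosing by about two thirds, to 112 days.

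The counts assume a completer who stays on one regimen with visits on nominal days; someone who switches regimen has an infusion count between the two. The size of the harm is unknown, because the documents give neither the number of WOCBP nor a quantified fetal risk. This is a worthwhile, inexpensive safety improvement and has no bearing on the validity of any analysis.

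**What to change.** In the pregnancy-test row of Table 1, add marks at weeks 16, 24 and 36 for WOCBP, with a note that the test is done on site and read before that day's infusion. All three are mandatory site visits with urinalysis already scheduled, and all are dosing weeks on both regimens. In SAP Section 6.3, add the three weeks to the pregnancy-test window table with the windows already set for urinalysis (days 2-141, 142-211 and 212-295).

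The cost is three kits per WOCBP: at most 3 × 30 = 90 if all of about 30 participants were WOCBP. The test needs an on-site read, because urinalysis samples go to the central laboratory (Section 8.3.4) and the result would not be back before dosing. A positive or unclear result would delay that infusion until confirmed. As with any schedule change, Table 1 would need a protocol amendment with the approvals in Section 10.1.1, and possibly re-consent under Section 10.1.3.

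If the sponsor also wants to shorten the first stretch, tests at weeks 4, 8 and 12 need no new visit. The longest untested stretch of dosing would then be 12 weeks (week 24 to 36), for at most 6 × 30 = 180 kits. If the sponsor prefers discretionary testing, the protocol should say why it is enough.

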- Treatment period: 48-week treatment period in which participants will receive efgartigimod doses either QW or Q2W based on their responder status. Switch points (ie, time points when clinESSDAI is conducted to determine responder status) will occur on day 1, week 16, and week 24. A participant who is not a responder on week 24 and classified by the PI as a nontherapeutic failure will continue QW dosing regimen until confirming the responder status. The participant will begin Q2W dosing regimen upon confirmation of the responder status
- 56-day follow-up period starting after the final IMP administration

Data Monitoring/Other Committee: No

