1.2. Schema

Abbreviations: D = day; IV = intravenous; QW = once weekly; Q2W = every 2 weeks; Wk = week.

^a QW or Q2W dosing regimen depending on responder status. Responders (defined as participants with a decrease in clinESSDAI of ≥ 3 points from baseline of qualifying study or who have a change clinESSDAI score that reclassifies their disease from moderate severity to mild severity) will be switched from QW to Q2W dosing regimen. Nonresponders will remain on QW dosing regimen. Switch points (ie, timepoints where clinESSDAI are conducted to determine responder status) will occur on day 1, week 16, and week 24. If a participant is not a responder at week 24, they will be evaluated by the PI for therapeutic failure. If not considered a therapeutic failure, the participant will continue QW dosing regimen and will return at weeks 32, 36, 40 and 44 for a clinESSDAI assessment until confirming the responder status and switching to Q2W dosing regimen or PI considers the participant to be a therapeutic failure. For QW regimen, the final dose will be administered at week 47. For Q2W regimen, the final dose will be administered at week 46.

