^k ClinESSDAI will only be conducted at weeks 32, 36, 40, and 44 if the participant is a nonresponder at week 24 and not considered a therapeutic failure by the PI.

^l The questionnaires should be performed before other study interventions and can be done one day in advance.

	BL ^a	Study week																EDV ^b	SFV ^c
		1	2	3	4	5-7	8	9-11	12	13-15	16	17-23	24	25-35	36	37-47	48		
Study day (±2)	1	8	15	22	29	36-50	57	64-78	85	92-120	127	134-162	169	176-246	253	260-330	337		393

^m The maximum total efgartigimod dose per efgartigimod IV infusion is 1200 mg for participants weighing ≥ 120 kg. The IMP weight-based dose will be recalculated if a participant’s weight has changed (increased or decreased) by more than 10% from OLE baseline (ie, weight prior to IMP infusion on day 1 of the ARGX-113-2211 study).

ⁿ The IMP infusion on day 1 will occur following eligibility check, informed consent signature, and baseline assessments.

^o Responders will reduce dosing frequency from QW to Q2W dosing regimen. Nonresponders will remain on QW dosing regimen. Switch points will occur at baseline, week 16, and week 24. The PI will evaluate a participant who is not a responder at week 24 for therapeutic failure. If the participant is not considered a therapeutic failure, QW dosing regimen will be continued, and the participant will return at weeks 32, 36, 40, and 44 for a clinESSDAI assessment up to confirming the responder status and switching to Q2W dosing regimen or if the PI considers the participant to be a therapeutic failure. For QW regimen, the final dose will be administrated at week 47. For Q2W regimen, the final dose will be administered at week 46.

^p If a participant who has reduced dosing frequency to Q2W considers their condition worsening, an unscheduled visit will occur during which a clinESSDAI and blood sampling for PK and ADA will be conducted. The participant will revert to QW dosing regimen for the remainder of the treatment period if there has been an increase in clinESSDAI score of ≥ 3 points and/or a change in score that reclassifies their disease from mild severity (clinESSDAI < 5) to moderate severity (clinESSDAI ≥ 5).

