6.3. Windowing Conventions

All assessments, including unscheduled assessments, will be allocated to an analysis visit window. Tables and listings will be based on analysis windows defined below. Allocations of assessments will be performed using their relative day.

Table B: Non-efficacy Analysis Visit Definition (immunogenicity)

Phase	Target Day	Assigned Study Day		Week Assigned
		Assigned (Inclusive) From	To	
Treatment	Not applicable ^a			Baseline
	15	1 ^a	22	Week 2
	29	23	43	Week 4
	57	44	71	Week 8
	85	72	99	Week 12
	113	100	141	Week 16
	169	142	211	Week 24
	253	212	295	Week 36
	337	296	Up to the date of SFV.	Week 48
Safety Follow-up	NA	NA	NA	SFV

confidential and proprietary to IQVIA Holdings Inc. and its subsidiaries. Unauthorized use, disclosure or reproduction is strictly prohibited.

^a Last available non-missing measurement from the parent study ARGX-113-2106.

For QW regimen, the final dose will be administrated at week 47. For Q2W regimen, the final dose will be administered at week 46.

After treatment period ends, safety follow-up will be approximately 7 weeks (56 days ± 3 days) will be summarized separately.

[figure not shown]
The above [Table B](#) contains visit window for every assessment's visited (e.g., Immunogenicity). Refer to respective visit window table for other assessments.

Some parameters which are not collected at every visit, visit window will be combined (by extending window with previous or subsequent visits).

[figure not shown]
For e.g. Week 2 are not protocol scheduled visit for brief physical examination (symptom driven), vital signs, electrocardiogram (ECG), clinical laboratory assessments, total IgG, anti-Ro/SS-A, anti-La/SS-B autoantibodies. Hence, visit window can be combined with baseline and week 4. The non-missing value closest to the target day will be used in the analysis in case of multiple observations.

Table B: Non-efficacy Analysis Visit Definition for brief physical examination (symptom driven), vital signs, electrocardiogram (ECG), clinical laboratory assessments, total IgG, anti-Ro/SS-A, anti-La/SS-B autoantibodies.

Phase	Target Day	Assigned Study Day (Inclusive)		Week Assigned
		From	To	
Treatment	Not applicable ^a			Baseline
	29	2	43	Week 4
	57	44	71	Week 8
	85	72	99	Week 12
	113	100	141	Week 16
	169	142	211	Week 24
	253	212	295	Week 36
	337	296	Up to the date of SFV.	Week 48
Safety Follow-up	NA	NA	NA	SFV

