17.1.1. Adverse Events

AEs and SAEs will be collected as defined in the [Section 10.3](#) of the protocol. Also, the AEs listed in previous study of ARGX-113-2106 which are “Ongoing” will be included for OLE study. AEs will be coded using latest version of Medical Dictionary for Regulatory Activities (MedDRA) central coding dictionary. AEs will be graded using the National Cancer Institute (NCI) Common Terminology Criteria for Adverse Events (CTCAE) version 5.0. For each AE, start and stop date/times are collected as well as severity, a seriousness flag, treatment-relatedness, relatedness to procedures, action taken towards the study drug and outcome.

Treatment-emergent adverse events (TEAEs) are defined as AEs with onset on or after the first administration of

Copyright © 2009, 2010, 2012, 2016, 2018, 2019, 2021, 2024 IQVIA. All rights reserved. The contents of this document are confidential and proprietary to IQVIA Holdings Inc. and its subsidiaries. Unauthorized use, disclosure or reproduction is strictly prohibited.

IMP up to and including 60 days after the last IMP administration before the event (refer to schematic).

D1: IMP start	D40: Start IMP interruption		D120: IMP restart	D160: Start IMP disc		D240: Study disc
IMP			IMP			
TE: D1-D40	TE: D40+60 days	Non-TE: D101-119	TE:D120-D160	TE: D160+60 days	Non-TE: >D220	

AEs will be considered treatment-emergent based on their start date/time. If the AE start date/time is incomplete or missing, the AE will be considered treatment-emergent unless the available part of the AE start or stop date/time provide evidence that the event did not occur within 60 days from last IMP administration before the event.

AE onset and duration will be calculated as follows when start and stop dates are fully known:

- AE onset day (versus first administration)
 - AE start date \geq date of first administration: AE start date – date of first administration + 1 day.
 - AE start date < date of first administration: AE start date – date of first administration.
- AE duration (days) =
 - AE end date – AE start date + 1 day.
 - study discontinuation date – AE start date + 1 day (when the AE start date is fully known but the AE is not resolved at the end of the study). In this case the duration will be presented as “>x days”.

An AE for which the study drug was discontinued is defined as an AE with action taken “drug withdrawn”.

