17.1.2.1. Laboratory Specific Derivations

All datapoints obtained after informed consent up to 60 days after IMP discontinuation will be considered.

- The following abnormality categories will be defined:
 - Low: value < lower limit of normal range
 - Normal: lower limit of normal range \leq value \leq upper limit of normal range
 - High: value > upper limit of normal range
- Notes:
 - Classification will be done in standardized units, using non imputed values and limits.
 - For the worst-case analysis visits, as defined in [Section 6.4](#), an additional category low + high is defined in case there are both low and high post-baseline values.

Toxicity grades will be computed according to the National Cancer Institute (NCI) common toxicity criteria for adverse events (CTCAE) toxicity grading list (version 5.0). The implementation of these toxicity grades for analysis is presented in [Appendix 2](#). Only the parameters described in [Appendix 2](#) will be computed, according to the declared limits for each grade.

Only lab parameters specified within the protocol will be analysed and, only those both in the protocol and in [Appendix 2](#) will be considered for toxicity. All others that are in the protocol and not in [Appendix 2](#), but have High/Low/Normal will be presented in the abnormality table.

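### Table 1 dates the safety follow-up visit 63 or 70 days after the final dose, the protocol's own rule says 56 ± 3 days, and the SAP's 60-day safety limits lie between the two

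*Protocol*

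**What the plan says.** **Timing of the SFV.** The study-day row of Protocol Table 1 (section 1.3) ends "260-330 337 393". These entries are weeks 37-47, week 48 and the SFV, and the row carries a ±2 day window. Footnote c, attached to the SFV column heading, reads "Participants will attend a safety follow-up visit 56 ± 3 days after the final IMP administration". Section 7.1.1 gives the same 56 ± 3 days. The synopsis describes a "56-day follow-up period starting after the final IMP administration". Section 4.1 also counts about 56 days from the final administration, but gives the maximum participation as about 56 weeks, made up of 48 weeks of treatment and 8 of follow-up.

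**Last dose.** The schema footnote (section 1.2) states "For QW regimen, the final dose will be administered at week 47", and week 46 for Q2W. Footnote o to Table 1 repeats both.

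**SAP limits.** Section 17.1.1 defines an event as treatment-emergent if it starts on or after the first administration of "IMP up to and including 60 days after the last IMP administration before the event". For laboratory data, section 17.1.2.1 says "All datapoints obtained after informed consent up to 60 days after IMP discontinuation will be considered". The ECG, vital-sign and physical examination sections (17.1.3, 17.1.4, 17.2.1) carry the same sentence. Section 6.3 lists the SFV as an analysis visit with no day limits, and says that after the treatment period "safety follow-up will be approximately 7 weeks (56 days ± 3 days", to be summarized separately.

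**The concern.** The table cell and its own footnote give different dates for the same visit. The table counts 56 days from the week 48 visit. The footnote counts them from the last infusion, which is one week (QW) or two weeks (Q2W) earlier. A participant who completes treatment with doses on the nominal days cannot satisfy both.

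This matters because the SAP's 60-day limit falls between the two dates. An SFV timed by the footnote is inside it, and an SFV timed by the table is outside it if the limit runs from the last infusion. Long-term safety is the primary objective, and enrollment is up to approximately 30 participants, so a few late events or values can change a safety table. The SFV is the last scheduled safety visit and the one furthest from dosing.

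**Working it through.** **Inputs.** Week 47 = day 330, week 48 = day 337, SFV = day 393 ± 2 (Table 1). SFV rule 56 ± 3 days (footnote c, section 7.1.1). Final dose at week 47 or week 46 (section 1.2, footnote o). TEAE limit 60 days after the last administration (SAP 17.1.1).

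**Study-day formula.** Day = 7 × week + 1. This reproduces the printed days for weeks 1, 2, 4, 8, 12, 24, 36, 37, 47 and 48. It does not reproduce week 16, printed as day 127 against 7 × 16 + 1 = 113, which is also the SAP's target day. Week 46 is not printed separately; the formula gives 7 × 46 + 1 = 323.

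**Reproducing the table's day.**
- Week 48 visit + 56: 337 + 56 = **393**, which matches.
- Week 47 dose + 56: 330 + 56 = 386, which does not.
- Week 46 dose + 56: 323 + 56 = 379, which does not.

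Of these anchors, only the week 48 visit gives the printed day.

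**Comparison at nominal dosing days.**

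| | QW | Q2W |
|---|---|---|
| Final dose | day 330 | day 323 |
| Footnote window (+53 to +59) | 383-389 | 376-382 |
| Table window (393 ± 2) | 391-395 | 391-395 |
| Last dose to day 393 | 393 − 330 = 63 | 393 − 323 = 70 |
| Last dose to table window | 61-65 | 68-72 |
| 60-day limit from last dose | 330 + 60 = 390 | 323 + 60 = 383 |
| Day 393 beyond that limit | 3 days | 10 days |

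**Allowing ±2 days on the final dose.** For QW, a dose on day 332 allows an SFV up to 332 + 59 = day 391, the first day of the table window. The two windows then just touch, at 59 days after the dose. For Q2W, the smallest gap is 391 − 325 = 66 days, so they never meet.

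**Adverse events.** Events are collected until the SFV (Protocol 8.4.1) and classified by start date (SAP 17.1.1). With an SFV on day 393, onsets on days 391-393 (QW, 61-63 days after the last dose) or 384-393 (Q2W, 61-70 days) are collected and listed but are not TEAEs.

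**Laboratory, ECG, vital-sign and physical examination data.** The result depends on what IMP discontinuation means for a participant who completes treatment:
- If it is the last infusion, the limit is day 390 or 383, and day 393 is outside.
- If it is the end of treatment at week 48, the limit is 337 + 60 = day 397, and day 393 is inside.

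**The SAP's own description.** 56 days is 56 / 7 = 8 weeks, not 7.

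**The case against.** The best defence is that footnote c sits on the SFV column heading, so anyone reading day 393 is sent straight to the dose-based rule. Sections 1.1, 4.1 and 7.1.1 use the same anchor, and a participant who stops early can be scheduled only by that rule. Day 393 can then be read as the nominal maximum stay of 56 weeks. On that reading the SFV falls 53-59 days after the last dose, inside the SAP's 60 days, and no data are lost. This stands: any harm requires a site, or a scheduling tool built from Table 1, to work from the day row.

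A reader might infer that every completer's SFV laboratory, ECG and vital-sign results would be lost. The documents do not support that. SAP 6.1 distinguishes treatment completion from permanent discontinuation of IMP, and the sentence on these data is not tied to the last infusion. SAP Table B also gives the SFV its own row without day limits. But the SAP does not say whether that row or the 60-day sentence prevails.

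Nor is the SFV the only safety assessment after dosing ends. The week 48 visit comes 7 or 14 days after the final dose and includes physical examination, vital signs, ECG, laboratory tests and urinalysis.

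On adverse events, a cut-off for treatment emergence is deliberate. An event reported at a late SFV still counts if it began within 60 days of the last dose, and later onsets remain in the listings.

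The objection narrows the consequence. It does not remove the contradiction between the table day and the rule.

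**Conclusion.** The concern holds as an inconsistency with a conditional effect on the analysis. At nominal dosing days, the table's SFV day is 7 days (QW) or 14 days (Q2W) later than the protocol's dose-based rule, and 3 or 10 days past the TEAE limit.

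- **If sites follow footnote c:** nothing is lost.
- **If sites follow the table day:** events starting 61-63 days (QW) or 61-70 days (Q2W) after the last dose leave the TEAE tables and stay in the listings. This does not depend on how IMP discontinuation is read, because the TEAE limit is tied explicitly to the last administration.
- **SFV laboratory, ECG, vital-sign and physical examination data under the table day:** excluded if the 60 days run from the last infusion, retained if they run from week 48. The SAP leaves this open.

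These figures assume completion of treatment on the planned schedule. Day 393 has no bearing on participants who stop early. The documents do not establish which SFV timing is intended, and this review takes no position on it.

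**What to change.** **Protocol.** Reconcile the SFV study day in Table 1 with footnote c and section 7.1.1, so that a site reads one instruction. Which timing to keep is the sponsor's decision.

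**SAP.**
- Bring the follow-up description in section 6.3 into line with the timing that is kept, and correct the equation of about 7 weeks with 56 days.
- In sections 17.1.2.1, 17.1.3, 17.1.4 and 17.2.1, define the date from which the 60 days run, for completers and for participants who discontinue.
- State that assessments labelled SFV are kept in the SFV safety summaries whatever their day. This settles the conflict with Table B.
- Check that the TEAE limit in section 17.1.1 covers the SFV timing that is kept, including its window.

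**Cost.** A protocol clarification by amendment or memo and a few sentences in the SAP. No new visits or data are needed.
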